## Objective II: Statistics

Individualized scale scores from each of the questionnaires, the MMPI-2, and the RTMITE, the scores from the Ultimatum Game, the number of points earned on the Balloon Task, and dependent measures (such as accuracy scores and reaction times) on the vigilance, memory, and reasoning tasks will be analyzed with a series of mixed-factorial ANOVAs. Significant main effects and interactions will be pursued with Analysis of Simple Effects followed by appropriate linear contrasts and pairwise comparisons.

On all assessments there will be 2 levels of the grouping factor: Intervention (Energy Deficit-Androgen Maintenance and Energy Deficit+Androgen Maintenance). For preliminary examination of immediate pre/post-dose effects (on tests other than MMPI), the primary analysis will include the single grouping factor of Intervention with two within-subjects factors: Dose-iteration (Dose2, Dose3, Dose4) and Pre-post (Pre-dose, Post-dose). For examination of cumulative treatment effects (on tests other than MMPI), the primary analyses will include the Intervention grouping factor (Energy

Deficit-Androgen Maintenance and Energy Deficit+Androgen Maintenance) and a single within-subjects factor labeled Session, minimally with 7 levels (Baseline, Intervention1, Intervention2, Intervention3, Intervention4, Recovery1, and Recovery2). The specific sessions chosen for this “cumulative-treatment-effect” analysis will depend on whether or not acute testosterone dose effects are found in the previously-described separate examination of immediate pre/post dose effects (described above). If acute post-dose effects appear to have occurred, the Sessions will consist of: Baseline-Day13, Live-In-Day21, Live-In-Day27, Live-In-Day34, Live-In-Day41, AdLib-Day54, and AdLib-Day83. In this case, note that all of the Live-In sessions are 6 days removed from (i.e., following) the testosterone dose administrations. If the preliminary analysis indicates no differences between the immediate pre/post dose administrations, an analysis may be performed on all of the data-collection sessions, or possibly only on the Live-In sessions that immediately follow each of the testosterone dose administrations (i.e., Baseline-Day13, Live-In-Day15, Live-In-Day22, Live-In-Day29, Live-In-Day36, AdLib-Day54, and AdLib-Day83. In this latter case, note that all of the Live-In sessions occur on the very next day after testosterone has been injected. With regard to the MMPI-2, since it is only to be administered twice, there will be 2 levels of the Intervention grouping factor and 2 levels of the Session within-subjects factor (Baseline, and End-Of-Intervention Day 40).

ReadiBand activity/sleep-monitoring data (sleep duration, sleep latency, and sleep efficiency) will be analyzed via a mixed factorial ANOVA for Intervention (Energy Deficit-Androgen Maintenance and Energy Deficit+Androgen Maintenance) by Period (Baseline, Live-In1, Live-In2, Live-In3, Live-In4, Live-In5, Ad-lib). In addition, average sleep data during the acclimation (free-living) phase will be more generally compared to average sleep data during the intervention and ad-libitum (free-living) phases with a 2x3 ANOVA. Significant interactions from both sets of analyses will be followed up with Analysis of Simple effects and appropriate post-hoc comparisons. Depending on the pattern of observed effects, a more fine-grained analysis (which would potentially include every night of ReadiBand data) may be conducted as well.

Polymorphism assays for genes related to behavior will be conducted using nucleotides extracted from whole blood collected at the initial or a subsequent blood sample (~ 1 mL). A series of polymorphisms associated with differences in the stress response, testosterone-related behavioral traits such as cooperation, completion and aggression, cognitive and endocrine function as well as skeletal muscle adaptive responses to stress will be assessed and may include (but not be limited to): OXTR, AVPR1a (social and emotional regulation) CRHR1 and FKBP5 (HPA axis reactivity); COMT, 5-HTTLPR, DRD2, GABRA6, TCAT (neurotransmitters); and BDNF (synaptic plasticity). All polymorphism assays analyses will be performed on a fee-for-service basis at the Lincoln Laboratory at MIT; all samples will be coded using participant number.

fMRI data will be managed locally by Pennington Biomedical's Imaging Core. Across the 6 tasks, fMRI data will be analyzed in conjunction with investigators/consultants at USARIEM. Data will be analyzed for Intervention (Energy Deficit-Androgen Maintenance and Energy Deficit+Androgen Maintenance) by Period (Baseline, Live-In1, Live-In2, Live-In3, Live-In4, Live-In5, Ad-lib) effects.

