## Objective II: Methodology

A comprehensive battery of questionnaires, evaluations, cognitive performance tests, personality assessment and the actigraphic assessment of daily spontaneous motor activity, sleep and circadian rhythms will be used to evaluate the effects of energy deficit and exogenous testosterone administration. Validated questionnaires will be used to examine fatigue and other aspects of mood such as depression, aggressive thoughts and perceived hunger. Risk-taking propensity and dominance will be evaluated using standardized objective procedures, and beliefs about other's feelings and intentions will be determined via a validated projective technique. Vigilance, memory and reaction time will be assessed with a standardized cognitive test battery that has established sensitivity to the impact of a wide array of real-world stressors typical of military operations. Questionnaires, evaluations, cognitive performance tests, and personality assessments are described below and can be found in Appendix K.

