#### Objective Risk Assessment Tests

The **Balloon Analogue Risk Task (BART)** is a computerized test designed to measure willingness to take risks versus "play it safe." It requires the participant to fill a simulated balloon with air. Points are given for maintaining the flow of air and keeping the volume of the balloon as full as possible. The more expanded the balloon gets, the more points are earned. However, all points are lost if the balloon is over-inflated and pops. The object of this task is to earn as many points as possible by keeping the balloon inflated without popping. Additionally, there is a risk-learning component to this task as some balloon colors pop with less inflation and others with more, while a third category is unpredictable. Standard administration of this task allows 30 trials. The BART takes approximately 10 minutes to complete and will be administered via computer software.

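### The Balloon task is analysed only as points earned, which rise and then fall as inflation increases, so points alone do not guarantee a direction for risk-taking

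*Combined protocol and SAP*

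**What the plan says.** Under Objective Risk Assessment Tests, the protocol introduces the Balloon Analogue Risk Task as one that "is a computerized test designed to measure willingness to take risks versus" playing safe. Objective II: Methodology makes the construct an intended one: "Risk-taking propensity and dominance will be evaluated using standardized objective procedures".

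The scoring is described in the same place as the task. "The more expanded the balloon gets, the more points are earned". "However, all points are lost if the balloon is over-inflated and pops". The participant's goal is a high score: "The object of this task is to earn as many points as possible by keeping the balloon inflated without popping". There are three kinds of balloon: "some balloon colors pop with less inflation and others with more, while a third category is unpredictable". A standard session has 30 trials.

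Objective II: Statistics lists what enters the mixed-factorial ANOVAs. For this task the entry is "the number of points earned on the Balloon Task". It names no measure of inflation and no count of popped balloons. The open-ended wording in that sentence, which gives accuracy and reaction time as examples, belongs to the vigilance, memory and reasoning tasks and does not extend to this one.

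**The concern.** A score used to measure risk-taking should move one way as risk-taking increases. Points earned do not have to. A cautious man banks small amounts on most balloons, and a bold man banks large amounts on few. Their totals can agree, and beyond some level of inflation the bolder man scores lower.

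Two results would then be hard to interpret. If the arms do not differ in points, they may not differ in risk-taking, or they may lie on either side of the peak. If one arm scores fewer points, it may have been more cautious or it may have popped more balloons. With points alone, a reader cannot tell these apart. The same score also enters the preliminary pre/post-dose comparison, which Objective II: Statistics uses to choose the sessions for the cumulative analysis.

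**Working it through.** The plan gives no sample size, power or effect size for this task, so there is no figure to reproduce. The check is on the shape of the score.

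**From the scoring rule alone.** A balloon that is not inflated earns nothing. A balloon inflated until it is certain to pop earns nothing. Levels in between earn something on average. Expected points therefore cannot increase with inflation throughout. Only the position and height of the peak need further assumptions.

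**Inputs for an illustration.** The 30 trials per session and the 25 participants per group come from the protocol. The pop rule is not in the documents, so it is assumed. "Pump" is also my unit, since the protocol speaks of inflation.

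**Uniform break point over N pumps.** A man who always aims for k pumps keeps the balloon with probability 1 − k/N. Expected points per balloon are E(k) = k(1 − k/N). With N = 64:

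| Target k | Balloons popped | E(k) | Over 30 balloons |
|---|---|---|---|
| 16 | 25% | 16 × 0.75 = 12.0 | 360 |
| 24 | 37.5% | 24 × 0.625 = 15.0 | 450 |
| 32 | 50% | 32 × 0.5 = 16.0 | 480 |
| 40 | 62.5% | 40 × 0.375 = 15.0 | 450 |
| 48 | 75% | 48 × 0.25 = 12.0 | 360 |

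The same increase of 8 pumps changes the 30-balloon total by +90 (16 to 24), +30 (24 to 32), 0 (28 to 36, both 472.5), −30 (32 to 40) or −90 (40 to 48). N = 8, 32 and 128 give the same shape, with the peak at N/2.

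**Constant chance h of popping per pump.** Here E(k) = k(1 − h)^k. With h = 0.05, the 30-balloon totals are 170 at 9 pumps, 215 at the peak of 19, and 162 at 38. The shape does not depend on the uniform rule.

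**What this can do to a comparison of arms.** I simulated 25 men per arm with N = 64, an assumed between-person SD of 6 pumps, and a two-sided t-test at 0.05 (3,000 runs).

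| Mean targets | Mean difference in points | Power on points |
|---|---|---|
| 16 v 32 | +118.9 | 0.99 |
| 20 v 28 | +60.0 | 0.67 |
| 28 v 36 | +0.2 | 0.05 |
| 24 v 40 | +0.7 | 0.06 |
| 36 v 44 | −60.5 | 0.45 |
| 32 v 48 | −118.8 | 0.94 |

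In every row the second arm takes more risk. Power on intended pumps was about 1.00 throughout. Intended pumps are not observed, however, and the outcome proposed under the fix was not simulated, so this comparison shows what points lose and not what the replacement would gain.

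These runs use one balloon type. They do not model the three colours, for which a man may learn separate targets.

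**The case against.** **Men may stay below the peak.** If every man did so in every session, points would rise with risk and could be read one way, as the first two rows of the simulation show. This stands, and it rules out saying that points cannot show the direction of an effect. But the plan does not state this condition, and points alone do not allow it to be checked.

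**The zero differences are a chosen case.** Pairs such as 16 and 48, or 24 and 40, are symmetric about the peak of an assumed curve. This also stands: they are a worst case. Other pairs lose less power, and some of those reverse the sign.

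**Practice.** A reader might infer that learning across sessions biases the comparison, because the task has a risk-learning component. The documents do not support that. The section on training and testing for the behavioural battery schedules six training sessions (days 0, 2, 4, 6, 8 and 10) before the Day 13 baseline. Learning shared by the randomized arms falls in the Session effect and not in the Intervention-by-Session comparison.

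**Misreading.** A reader might also infer that the plan will report a fall in points as less risk-taking. It states no such rule; it gives no directional reading at all.

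**Importance.** The Objective II aims and hypotheses name mood, fatigue, personality, cognition and sleep; risk-taking appears as an assessed behaviour in the methodology. fMRI Task 1, a gambling task, separately addresses risky choice, so the trial's question does not rest on the Balloon score alone. Both points limit the weight of the concern. A second instrument does not repair the first one's score.

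**Conclusion.** The concern holds in a limited form. The only Balloon outcome in the plan is not monotone in the construct it is meant to measure. A difference in points has no guaranteed sign for risk-taking, and a real difference between arms near the peak can leave points almost unchanged. That much follows from the protocol's own scoring description.

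The size depends on assumptions: the pop rule, the 64-pump limit, the SD of 6 pumps and a single balloon type. Under these, power on points ranges from about 0.05 for arms straddling the peak to 0.99 for arms on its rising side. Where participants will lie is unknown, so no single figure should be attached to this trial.

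It does not follow that the Balloon analysis is uninformative, or that the trial cannot address risk-taking. This is one Objective II outcome, remote from the lean body mass endpoint on which the sample size rests.

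**What to change.** In Objective II: Statistics, replace the Balloon entry with wording such as: mean inflation (pumps) on balloons that did not pop is the risk-taking outcome, reported jointly with the number of popped balloons, by balloon colour where available; points earned are a secondary performance score.

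The two measures must be read together. The mean over unpopped balloons drops the trials on which most risk was taken and is truncated by the pops, so it can understate inflation in a man who pops often. The pop count shows when that is happening.

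The cost is a short change to the analysis text, with no extra testing, provided that the software stores inflation and pops for each trial. The task is computerized and its points depend on both, but the documents do not say what is exported, so this should be confirmed first. If only totals are kept, points should be reported as performance, without a claim about the direction of risk-taking.

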### **Objective I: Statistics**

All data analyses will be based on the intention-to-treat principle using SPSS statistical software, unless otherwise noted. Data will be examined quantitatively and graphically for outliers and other artifacts that might have an undue impact on the analyses. Logarithmic or similar transformations will be applied when necessary to insure the validity of statistical procedures. All tests will be two-sided and considered statistically significant at  $p < 0.05$ .

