**28-d Energy deficit testing:** Once the live-in, intervention portion of the protocol begins, volunteers will be asked to complete all of the subjective questionnaires (excluding the MMPI—see below), and risk/cognitive tests at 8 different points prior to the time at which they will return to free living. These cognitive test sessions will occur on Days 15, 20, 22, 27, 29, 34, 36, and 41. Note that 3 pairs of these sessions (D20 and D22, D27 and D29, and D34 and D36) are positioned so that they immediately surround the second, third, and fourth testosterone (or placebo) administrations on days 21, 28, and 35 in order to facilitate the examination of acute pre/post dose effects. Session on D15 occurs on the same day as the first injection. A determination regarding which sets of sessions will most appropriately describe the overall cumulative impact of the testosterone/calorie-deprivation intervention will depend on whether or not a preliminary analysis indicates the presence of significant differences between the 3 pairs of pre/post testosterone-administration sessions. Regardless of the outcome of this analysis, the session on Day 41 which is 1 day prior to the end of the entire intervention cycle (and 6 days after the final testosterone dose administration) will provide a valid end-point assessment of any cumulative calorie-deprivation/testosterone effects. With regard to the MMPI-2, it will be administered only on a single pre-intervention day (Day 5) and a single near-end-of-intervention day (Day 40) to explore the impact of caloric restriction and testosterone supplementation on several of the more stable aspects of personality.

**Recovery/Ad-libitum feeding testing:** During the final portion of the protocol, volunteers will be asked to complete two final questionnaire/test assessment sessions. The first will be on Day 54, and the second will occur at EOS.

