#### Psychological outcomes

Questionnaires will be scored according to questionnaire-specific procedures. Scores will then be analyzed by mixed-model repeated measures ANOVA. Mixed-models will include subject as a random factor, test session or study day and group as fixed factors, and the session-by-group or day-by-group interaction. Akaike's information criterion will be used to determine appropriate covariance structures. When a statistically significant time-by-group interaction is detected ( $P < 0.05$ ), all possible within- and between-group comparisons will be completed, and the familywise error rate adjusted using the Bonferroni correction.

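### Objective II names mixed-factorial ANOVAs over seven or more sessions with no missing-data rule; run classically, they would exclude any man lacking a score at one session

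*Combined protocol and SAP*

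**What the plan says.** Under Objective II: Statistics, the questionnaire, MMPI-2, RTMITE, Ultimatum Game, Balloon Task and cognitive scores "will be analyzed with a series of mixed-factorial ANOVAs", followed by simple effects, contrasts and pairwise comparisons. The cumulative-effect analysis crosses Intervention with "a single within-subjects factor labeled Session, minimally with 7 levels". If no acute dose effect appears, "an analysis may be performed on all of the data-collection sessions". Sleep measures "will be analyzed via a mixed factorial ANOVA for Intervention" by Period, with seven Periods listed. The section names no random subject effect, covariance structure, estimation method, missing-data rule or analysis set.

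The session schedule is in the Objective II methodology. Baseline is Day 13. For the live-in phase, "These cognitive test sessions will occur on Days 15, 20, 22, 27, 29, 34, 36, and 41". For recovery, "The first will be on Day 54, and the second will occur at EOS".

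The other two objectives describe a different model. Objective I (Physiological outcomes) and Objective III A-B (Physiological and Psychological outcomes) use subject as a random factor, study day or session and group as fixed factors with their interaction, and a covariance structure chosen by Akaike's information criterion (AIC). Objective III applies this to questionnaires: "Scores will then be analyzed by mixed-model repeated measures ANOVA".

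The intention-to-treat statement is in Objective I: Statistics: "All data analyses will be based on the intention-to-treat principle using SPSS statistical software, unless otherwise noted".

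**The concern.** The classical mixed-factorial (split-plot) ANOVA needs a score from each man at every level of the within-subject factor. A man with one empty level leaves the whole analysis, and his other scores go with him. With seven or more levels, of which the last two fall after discharge, a man could complete all 28 days of the deficit, miss Day 54 or EOS, and contribute nothing to the between-arm comparison during the deficit.

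The plan itself gives reason to expect gaps. The Power analysis allows for 20% attrition. Stopping Rules names dropout and missing data as a possible limit on the analysis, without saying how they will be handled. Primary Study Endpoint foresees procedures that are refused or cannot be done. The energy-deficit entry under Risks to Subjects has the PI and medical investigator review whether a man in psychological distress should continue. Mood and fatigue are Objective II outcomes, so leaving the study can be related to the outcome being measured. Restricting the analysis to men with complete data discards scores already collected and makes the comparison more exposed to that kind of dropout.

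**Working it through.** **1. The plan's own figure.** The only sample-size figure is for lean body mass (Table 2): 3.0 against 2.25 kg, SD 0.75, two-sided alpha 0.05, power 0.90. The normal approximation gives n = 2 × (1.960 + 1.282)² / 1.0² = 21.0, rounded up to 22 per group. An exact t calculation at 22 gives power 0.8997. The 22 reproduces. No Objective II outcome has an effect size or a power target.

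**2. Levels per analysis.**
- Cumulative effect: at least 7. If all sessions are used, 1 (Day 13) + 8 (live-in) + 2 (Day 54, EOS) = 11.
- Sleep by Period: 7.
- Pre/post-dose: 3 dose iterations × 2 = 6 cells.
- Averaged sleep comparison: 3 phases.
- MMPI-2: 2.

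**3. Men kept if only complete cases are analysed.** Formula: N × (1 − d) × (1 − m)^s, with N = 60 (Power analysis), d = dropout before the last session, m = missed rate per session and s = number of sessions. The value of m is an assumption, taken as independent across sessions; the documents give none.

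| d | m | s | Men kept |
|---|---|---|---|
| 20% | 0 | any | 60 × 0.80 = 48.0 |
| 20% | 2% | 7 | 48 × 0.98⁷ = 41.7 |
| 20% | 3% | 7 | 48 × 0.97⁷ = 38.8 |
| 20% | 2% | 11 | 48 × 0.98¹¹ = 38.4 |
| 10% | 0 | any | 60 × 0.90 = 54.0 |
| 10% | 2% | 7 | 54 × 0.98⁷ = 46.9 |

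The 10% row uses the dropout that Stopping Rules reports for similar studies. If sessions are missed only at the two free-living visits, 20% dropout leaves 48 × 0.98² = 46.1 or 48 × 0.97² = 45.2. Starting instead from the 50 completers the plan requires, 2% over seven sessions leaves 50 × 0.98⁷ = 43.4.

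**4. What a likelihood-based mixed model would keep.** Every randomised man with at least one usable score, so up to 60.

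**5. Labels against schedule.** The session list used when acute dose effects are found includes Live-In Day 21, but the schedule has no cognitive session that day. Both session lists end at Day 83, whereas the last session is at EOS, which varies by man. Under a complete-data method, a literal Day 21 level would be empty for everyone.

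**The case against.** **Deletion is not stated.** The section names a design, not an estimation procedure, and Objective I also uses the word ANOVA for its random-subject model. A reader might infer that the plan drops men with a missed session; no sentence says so. This stands as a limit on the claim. Even so, the classical reading is the natural one, because the other two objectives write out the random-subject model and this one does not. If a mixed model was meant, the text still needs to say so.

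**The intention-to-treat promise may not reach here.** A reader might conclude that Objective II breaks a commitment. The sentence speaks of all analyses but sits under Objective I and allows exceptions. Objective III repeats the surrounding paragraph without it, the Data Analyses section points to each objective's own text, and Withdrawal of Subjects expresses only a wish to analyse everyone. The conflict is therefore conditional.

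**Not every analysis is exposed alike.** The MMPI-2, pre/post-dose and three-phase sleep analyses have fewer than seven levels. Actigraphy is continuous, so one lost night need not empty a Period. Phase 2 is live-in and all measures are required, so most loss would come from dropout and the two recovery sessions.

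**The size is uncertain.** The 20% is an allowance. Its 48 men fall below the plan's own requirement of at least 50 completers. The 2–3% missed rate is assumed.

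**Bias and power.** It is tempting to say that the arm comparison will be biased or to quote a loss of power. The documents do not suggest that dropout will differ by arm, and they give no Objective II effect size. A mixed model cannot restore 30 men per arm at late sessions, because dropouts have no scores there.

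**Conclusion.** The point holds in conditional form. Objective II names a method that, run classically, keeps only men with a score at every level, and it states no missing-data rule or analysis set although attrition is allowed for. If the intention-to-treat sentence covers Objective II, the two are at odds.

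For the seven-session analysis, 20% attrition alone would leave 48 of 60 men, and an assumed 2% or 3% missed rate would lower this to about 42 or 39. With the 10% dropout seen in similar studies the starting figure is 54. These counts illustrate the mechanism and do not forecast the loss.

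Neither the primary endpoint (total body mass) nor the outcome used for sample size (lean body mass) is affected. The change is still worth making, because the plan already uses the better method elsewhere. A mixed model would reduce, but not remove, bias from dropout that depends on unobserved mood or fatigue.

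**What to change.** In Objective II: Statistics, replace the mixed-factorial ANOVA with the mixed-model form used in Objectives I and III: subject random; group, session (or period) and their interaction fixed; covariance structure chosen by AIC. In the pre/post-dose analysis, keep Dose-iteration and Pre-post as crossed fixed within-subject factors, with Intervention as the group factor, so that structure is not lost.

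Add a sentence that the models are fitted by likelihood (REML) to all randomised men with any available data. This is new text: the Objective I and III sections state neither the estimation method nor that analysis set.

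In the same edit, reconcile Live-In Day 21 and AdLib Day 83 with the session schedule in the Objective II methodology.

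The cost is wording in one section. It needs no new data, visits or software.
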